8.4 Observed Maltol, Maltol Glucuronide, Serum Iron, and TSAT

The observed values for maltol, maltol glucuronide, serum iron, and TSAT will be summarized by dose group and by visit/timepoint for FAS/ITT Population using the flowing descriptive statistics: n (the number of subjects), arithmetic mean, minimum and maximum.

The change from baseline values of serum iron and TSAT will be summarized by dose group for each post-baseline visit/timepoint for FAS/ITT Population using the flowing descriptive statistics: n (the number of subjects), arithmetic mean, median, minimum and maximum.

The observed data for maltol, maltol glucuronide, serum iron, and TSAT will also be listed by dose group for each individual subject for FAS/ITT Population.

For maltol and maltol glucuronide, the mean observed plasma concentrations will be plotted on a linear and semi-logarithmic scale against nominal time range by dose group and visit. Geometric mean observed plasma concentrations will be plotted on a linear scale against nominal time range by dose group and visit. Combined observed plasma concentrations will be plotted on a linear and semi-logarithmic scale against actual timepoint for each dose group and visit.

For serum iron, the mean observed serum concentrations will be plotted on a linear and semi-logarithmic scale against nominal time range by dose group and visit. Combined observed serum concentrations will be plotted on a linear and semi-logarithmic scale against actual timepoint for each dose group and visit. The change of baseline will be plotted similarly.

Mean observed TSAT will be plotted on a linear scale against nominal time range by dose group and visit. Combined observed TSAT will be plotted on a linear scale against actual timepoint for each dose group and visit. The change of baseline will be plotted similarly.

The concentration plots described above will be prepared based on the actual data, if applicable.

8.5 Population Pharmacokinetic Modelling

The FAS/ITT Population will be used for the PPK analysis.

8.5.1 Basic Model Construction

The maltol and maltol glucuronide concentrations will be analysed simultaneously by means of fitting the compartment models to observed concentration data using a population PK (PPK) approach.

Likewise, the serum iron and TSAT concentrations will be analysed. If the PPK modelling for TSAT is not feasible, population PD (PPD) approach may be performed.

Population PK models will be built using a nonlinear mixed effects modelling technique with NONMEM® software. It is planned that the first order conditional estimation with interaction (FOCEI) method will be used for model development. If this is not feasible (i.e. the model will fail to converge), the first order conditional estimation (FOCE) and the first order (FO) method will be used instead.

Different models will be attempted to fit the PK concentration-time data. The models will include, but are not limited to, one-compartment linear model, one-compartment linear model with first order absorption, two-compartment linear mammillary model, two-compartment linear mammillary model with first order absorption, three-compartment linear model, and three-compartment linear model with first order absorption, linear compartment model with zero order absorption or saturable absorption. Furthermore, a nonlinear compartment model may also be tested, if possible.

For each individual model, model stability will be assessed with the following:

- Model parameter estimates not close to a boundary;
- Shrinkage for interindividual variability terms (ETA) and residual unknown variability (EPS) < 30%;
- Condition number (ratio of the largest to the smallest eigenvalues) < 1000; and
- Correlation less than 0.90 between any two parameter estimates.

For the final PPK model, diagnostic plots will be presented and assessed.

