12 STATISTICAL CONSIDERATIONS

12.1 SAMPLE SIZE AND POWER CALCULATIONS

Pharmacokinetic data from the pivotal GCP PK studies conducted in both IBD patients and patients with IDA of any cause demonstrated that uptake of maltol and iron into the plasma after administration of Ferric Maltol display completely independent absorption profiles (studies ST10-01-101 and ST10-01-102). In study ST10-01-101, the PK and iron uptake of Ferric Maltol was investigated in blood and urine after single and repeated twice daily oral doses of 30 mg, 60 mg and 90 mg for 8 days in subjects with iron deficiency (with or without anaemia) through measurement of serum iron, TSAT, ferritin, total iron binding capacity, and soluble transferrin receptor, as well as plasma and urine concentrations of maltol and maltol glucuronide. In sub-study ST10-01-102, the PK and iron uptake of Ferric Maltol after a 30 mg single dose administered at steady-state were investigated in patients already being treated in the open label phase of studies ST10-01-301 or ST10-01-302 through measurement of serum iron, transferrin, TSAT, total iron binding capacity, ferritin, soluble transferrin receptor, plus plasma and urine concentrations of maltol and maltol glucuronide.

In sub-study ST10-01-102, with 15 IBD patients participating in the open-label phase of studies ST10-01-301 and ST10-01-302, plasma concentrations of maltol above the limit of assay detection were transiently observed between 15min and 4h after dosing (mean Cmax 67.3ng/mL; median Tmax 1.0h; mean AUC 136h*ng/mL; mean $t_{1/2\text{term}}$ 0.8h). However, consistent with earlier studies of ST10, maltol glucuronide predominated in plasma (mean Cmax 4677ng/mL; median Tmax 1.0h; mean AUC 9651h*ng/mL and mean $t_{1/2\text{term}}$ 1.1h). Maximal change in serum iron and TSAT was observed 2h after dosing, however in many subjects it was apparent from the TSAT rises that iron uptake was occurring from 30 minutes. The inter-subject variability for AUC of both maltol and maltol-glucuronide in this cohort was low (approximately 27%).

Therefore, as agreed with the EU CAs in the PIP, the inclusion of 36 subjects aged 10-17 years (12 per treatment group) in this study is considered to be adequate to characterise the iron uptake and PK parameters for the range of Ferric Maltol doses in an iron deficient adolescent population (with or without anaemia).

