12.2.1 Primary Endpoint Analysis

The primary endpoints for the study are pharmacokinetic parameters

1. Population PK analysis (PPK) of maltol and maltol glucuronide in plasma from PK samples collected on Day 1 (after first morning dose) and Day 10 (after last morning dose). Parameters to be derived and reported for each Ferric Maltol dose will be:

C_{max} , $C_{ave(0-6h)}$, $AUC_{(0-6h)}$, $AUC_{(0-inf)}$ on Day 1 and Day 10, and ratios of Day 10/Day 1 for these parameters.

T_{max} , half-life ($t_{1/2}$).

Apparent systemic clearance (CL/F), apparent volume of distribution (V/F).

Descriptive statistics for plasma concentrations of maltol and maltol glucuronide by time of collection on Day 1 and Day 10 will also be presented, including C_{trough} .

2. Descriptive and population PK analysis of serum iron and TSAT from PK samples collected on Day 1 and Day 10. Parameters to be derived and reported for each Ferric Maltol dose will be:

Change from pre-dose (C_{trough}) to maximum post-dose (C_{max}) value for serum iron and TSAT; $C_{ave(0-6h)}$.

Pre-dose adjusted Incremental $AUC_{(0-6h)}$ on Day 1 and Day 10 from a population PK analysis approach, and percentage change from Day 1 to Day 10.

Apparent systemic clearance (CL/F), apparent volume of distribution (V/F).

Descriptive statistics for serum iron and TSAT by time of collection on Day 1 and Day 10 will also be presented.

Population PK models will be built using a nonlinear mixed effects modelling technique with NONMEM® software. It is planned that the first order conditional estimation (FOCE) method will be used for model development. If this is not feasible (i.e. the model will fail to converge), the first order (FO) method will be used instead. Different models will be attempted to fit the PK concentration-time data. The models will include but not limited to one-compartment linear model, one-compartment linear model with first order absorption, two-compartment linear mammillary model, two-compartment linear mammillary model with first order absorption, three- compartment linear model, and three-compartment linear model with first order absorption.

For each individual model, model stability will be assessed with the following:

- Model parameter estimates not close to a boundary;
- Shrinkage for interindividual variability terms (ETA) and residual unknown variability (EPS) < 30%;
- Condition number (ratio of the largest to the smallest eigenvalues) < 100; and

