4.2 Primary Pharmacokinetic Measurements and Variables

4.2.1 PK blood sampling

On study days 1 and 10, all subjects were to have baseline (pre-dose) PK blood samples collected immediately prior to Ferric Maltol dosing (0h). Subjects were then to have further PK blood samples collected at two additional times between 0.5h and 6h after dosing on Days 1 and 10; within each Ferric Maltol dose group (7.8 mg, 16.6 mg or 30 mg BID), the post-dose PK sample time collection windows were 0.5-1h, 1.0-2.0h, 2.0-3.0h, 3.0-4.0h and 4.0-6.0h. The 12 subjects within each Ferric Maltol dose group were assigned to the required post-dose PK blood sampling schedule in sequential order at the time of randomisation, based on current subject enrolment across all study sites. Table 3 details the sparse PK blood sample schedule.

Table 3 Sparse PK Blood Sampling Schedule

	PK Sample Schedule			
	Group 1 (N = 3/12)	Group 2 (N = 3/12)	Group 3 (N = 3/12)	Group 4 (N = 3/12)
Pre-dose (0h)	X	X	X	X
0.5 – 1h	X	X		
1.0 – 2.0h	X		X	
2.0 – 3.0h		X		X
3.0 – 4.0h			X	
4.0 – 6.0h				X

For each individual subject, the post-dose PK blood sampling schedule was to be the same on Day 1 and Day 10. Post-dose samples for each subject were to be collected within the allocated time-windows (e.g. between 0.5-1h or 1-2h); the exact time of the sample collection was to be recorded in the eCRF. For those subjects in PK Sample Schedule Group 1 (see Table 3), the PK blood samples for the 0.5-1h timepoint window were to be taken at 30 minutes prior to the PK blood samples for the 1-2h timepoint window on Day 1 and Day 10, to provide an adequate spread of actual sampling times for the population PK analysis.

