8.5.4 Concentration Prediction and Parameter Derivation

The serum iron, plasma maltol, plasma maltol glucuronide concentration, and TSAT versus time profile on Days 1 and 10 will be predicted for each subject using the individual PK parameters estimates from the final model.

Standard non-compartmental methods (NCA) will be used for the PK parameter calculations based on the predicted concentrations. The Linear Up Log Down method (equivalent to the Linear Up/Log Down option in WinNonlin® Professional) will be used in the computation of AUC.

Maltol and maltol glucuronide:

The following parameters for Day 1 will be derived for each Ferric Maltol dose based on the predicted maltol and maltol glucuronide concentrations, if applicable:

Table 4 Parameters for Maltol and Maltol Glucuronide on Day 1

Parameters	Description
C_{\max}	Maximum plasma concentration directly from data
T_{\max}	Time to reach maximum concentration directly from data
λ_z	Apparent first-order terminal elimination rate constant
$t_{1/2}$	Terminal elimination half-life, calculated as $\ln(2)/\lambda_z$
AUC_{0-6h}	Area under the plasma concentration versus time curve from time zero to 6hr.
$AUC_{0-\infty}$	Area under the plasma concentration versus time curve from time zero extrapolated to infinity time
CL/F	Apparent clearance calculated as Dose/ $AUC_{0-\infty}$
V_z/F	Apparent volume of distribution (as Dose/ $[\lambda_z * AUC_{0-\infty}]$)

The following parameters for Day 10 will be derived for each subject based on the predicted maltol and maltol glucuronide concentrations, if applicable:

Table 5 Parameters for Maltol and Maltol Glucuronide on Day 10

Parameters	Description
Tau	The dosing interval for steady-state data tau=12
C_{max}	Maximum concentration between dose time and dose time + Tau. If not unique, then the first maximum is used.
C_{trough}	Minimum concentration between dose time and dose time + Tau
T_{max}	Time to reach C_{max} during a dosing interval
AUC_{0-6h}	Area under the plasma concentration versus time curve from time zero to 6hr.
AUC_{0-tau}	Area under the plasma concentration versus time curve from time zero to Tau
$C_{ave(0-6h)}$	Average Steady State Plasma Concentration from 0-6h, calculated as AUC_{0-6h} divided by 6
CL_{ss}/F	Apparent clearance calculated as Dose/ AUC_{0-tau}
R_{Cmax}	Accumulation ratio based on maximum concentrations after first dose and last dose, calculated as $C_{maxDay10}/C_{maxDay1}$

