13 SAMPLE SIZE AND POWER CONSIDERATIONS

No formal sample size calculation has been carried out for this study. The sample size is based on observations from previous studies (see protocol for more details) and has been agreed with the EU CAs in the PIP. The inclusion of 36 subjects aged 10-17 years (12 per treatment group) is considered to be adequate to characterize the iron update and PK parameters for the range of Ferric Maltol doses in an iron deficient adolescent population (with or without anaemia).

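### The estimation chain ends in NONMEM's FO method with no limit on reporting from it; FO can bias V/F and half-life upward, by an amount the documents do not pin down

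*SAP*

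**What the plan says.** SAP 8.5.1 sets the first choice: "It is planned that the first order conditional estimation with interaction (FOCEI) method will be used for model development". On non-convergence, "the first order conditional estimation (FOCE) and the first order (FO) method will be used instead". The natural reading is a sequence of FOCEI, then FOCE, then FO. Protocol 12.2.1 and the Synopsis start at FOCE, and if that fails "the first order (FO) method will be used instead".

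The reported parameters are not the population values themselves. Under SAP 8.5.4, profiles "will be predicted for each subject using the individual PK parameters estimates from the final model", and then "Standard non-compartmental methods (NCA) will be used for the PK parameter calculations based on the predicted concentrations". Half-life and V/F (SAP Table 4) come from the terminal slope and AUC of those predicted profiles.

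The data are sparse. Besides the pre-dose sample, each child has "further PK blood samples collected at two additional times between 0.5h and 6h after dosing on Days 1 and 10", in one of four schedules with three children per schedule per dose group (SAP Table 3).

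Neither document restricts reporting from an FO fit, asks for a bias check, or names a last resort other than FO.

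**The concern.** FO expands the model around the typical child, with all random effects at zero, and so fits the typical curve to the population mean. For a nonlinear model the two differ. When children differ in absorption and elimination rates, the mean curve is flatter and longer-tailed than the typical child's curve, and FO can read this as a larger volume and slower elimination. This error does not shrink as children are added.

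The branch could be reached. The plan itself provides for non-convergence, it fits maltol and its glucuronide simultaneously, and its candidate models run to three compartments and saturable absorption, all on two post-dose samples per child per day. V/F and half-life are primary parameters, and Protocol 5.5 says that the study's data will select the Phase 3 paediatric dose(s).

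**Working it through.** The documents give no bias figure to reproduce, and SAP 13 states that there was no formal sample size calculation. The check is therefore by simulation.

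**Inputs from the documents**
- Adult half-life and Tmax: glucuronide 1.1 h and 1.0 h; maltol 0.8 h and 1.0 h (Protocol 5.4, 12.1).
- Between-subject variability: about 27%, for AUC only, in 15 adults (Protocol 12.1).
- Sampling: the four schedules of SAP Table 3 on both days, with times uniform within windows.

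**Assumed**
- One compartment with first-order absorption and log-normal variability.
- The SDs on V/F and ka, and independence of CL, V and ka unless stated otherwise.
- Proportional residual error of 20%.

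**Step 1, typical values.** ke = ln 2 / half-life = 0.693/1.1 = 0.63 per h (glucuronide) and 0.693/0.8 = 0.87 per h (maltol). Solving Tmax = ln(ka/ke)/(ka - ke) = 1.0 h gives ka = 1.49 and 1.15 per h.

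**Step 2, the FO fit.** Each child's data vector is treated as normal, with mean f(θ, η = 0) and variance GΩG' + R, where G is the derivative of f with respect to η at zero.

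**Step 3, bias of the FO population estimates with 4000 simulated subjects**

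| Variability | Glucuronide V/F | Glucuronide half-life | Maltol V/F | Maltol half-life |
|---|---|---|---|---|
| 27% each on CL, V, ka | +15% | +17% | +31% | +35% |
| 27% on CL and V, 50% on ka | +23% | +26% | +47% | +52% |
| 27% on CL, almost none elsewhere | +7% | +11% | +15% | +19% |
| 27% in bioavailability only | -4% | 0% | -4% | 0% |
| 27% in bioavailability, 27% on ka | 0% | +4% | +6% | +9% |
| 27% each on CL, V, ka; fit on log concentrations | +5% | -2% | +12% | +5% |

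Half-life here is ln 2 × V/CL. In row 1 for glucuronide, V is +14.7% and CL is -2.1%, so 1.147/0.979 = 1.17. Other runs of the first two scenarios gave glucuronide V/F up to +25% and half-life up to +30%, and maltol half-life up to +57%. With faster glucuronide absorption (ka 3 to 5 per h) and row 1 variability, V/F bias is +7 to +10% and half-life bias +12 to +13%.

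**Step 4, is FO the cause?** Both methods were fitted to the same 1000 subjects under row 1 variability:
- Glucuronide: FO gave V/F +15.3% and half-life +19.8%; FOCEI gave +2.9% and -0.3%.
- Maltol: FO gave +32.5% and +39.2%; FOCEI gave +1.7% and -1.1% (the FOCEI optimiser did not report convergence).

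On a separate glucuronide data set of 400 subjects (50% on ka), exact maximum likelihood gave V/F -5% and half-life -3%; FO gave +22% and +32%.

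**Step 5, individual values, which feed the reported parameters.** Under row 1 variability, glucuronide V is +12 to +15% and half-life +10 to +15%. Maltol V is +27 to +32% and terminal half-life +17 to +19%. For glucuronide with ka 3 per h the individual bias falls to about +5% (V) and +3% (half-life).

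**Step 6, effect on AUC and Cmax.** Take a glucuronide FO fit to 3000 subjects under row 2 variability: V/F +22%, ka +32%, CL/F -2%. In the typical profile, AUC(0-inf) changes by 1/0.98 = +2%, AUC(0-6h) by -0.6% and Cmax by -4%, and Tmax moves from 1.00 to 0.93 h. The same errors applied at ka 3 per h give AUC(0-6h) -0.7% and Cmax -8%. The V and ka errors largely offset each other. Across the untransformed fits at 27%, CL/F bias was about -2 to -8%.

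**Step 7, at the planned size.** In 100 simulated trials of 36 children (glucuronide, row 1), median bias was V/F +14% and half-life +17%. The 5th to 95th percentile range for half-life was -14% to +46%.

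**The case against.** - **FO is only the last resort.** This stands. In the SAP two methods must fail first, and no failure rate has been estimated. A reader might infer that non-convergence leads straight to FO; the SAP does not say that. FO is still where the chain ends, with no condition on its use.
- **No single bias figure is supported.** This also stands. A reader might infer a bias of about 20% as a property of the sampling scheme at adult-like variability. The documents give no variability for V/F or ka, no correlation and no residual error. At the same 27%, half-life bias runs from about 0 to over 50%. The one-compartment model is itself approximate: set to adult half-life, Tmax and AUC, it predicts Cmax of about 3240 ng/mL for glucuronide and 50 ng/mL for maltol, against 4677 and 67.3 in the protocol. Maltol and glucuronide were simulated separately, although the SAP fits them together. Serum iron and TSAT were not simulated.
- **The derived parameters are mostly safe.** This is largely right. A reader might infer that every parameter in SAP 8.5.4 inherits the error. Step 6 shows that AUC and Cmax barely move.
- **With 36 children the noise exceeds the bias.** True, but the median remains +17%, and a systematic error adds to the noise.
- **The plan already has checks.** SAP 8.5.1 lists boundary, shrinkage, condition-number and correlation criteria and diagnostic plots, and allows other structural models. None of these criteria tests for linearisation bias, so a biased FO fit could pass them.

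**Conclusion.** The point holds in limited form. FO is an unguarded last resort for primary parameters, and it can bias V/F and half-life upward where FOCEI or exact likelihood on the same data does not.

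- **Independent variability on CL, V and ka (27%, or 50% on ka):** glucuronide about +15 to +25% for V/F and +20 to +30% for half-life. Maltol is larger, over +50% for half-life with 50% on ka.
- **Variability mainly in bioavailability, or a log-scale fit:** near 0 to about +10%.
- **Individual glucuronide values:** somewhat less, about +10 to +15% with 27% on each parameter, and less again if absorption is faster.
- **CL/F, AUC and Cmax:** a few percent, up to about 8%.

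All sizes rest on the assumed one-compartment model, the assumed variability and the 20% residual error. They apply only if FOCEI and FOCE both fail. The issue warrants a change because two primary parameters are exposed and the remedy is cheap.

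**What to change.** In SAP 8.5.1, replace the FO step with SAEM or importance sampling, both available in NONMEM. If that is also unstable, simplify the random-effects or structural model. Use FO only to obtain starting values. If an FO fit is nevertheless reported, label its V/F and half-life as FO-based and attach a bias check, for example by simulating from the fitted model and re-estimating. List the departure from Protocol 12.2.1 in SAP 14, which now declares no changes.

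The cost is small: a paragraph of SAP wording, a fixed random seed, a convergence check for the stochastic method, and some computing time.

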$R_{AUC0-6h}$	Accumulation ratio based on AUC_{0-6} after first dose and last dose, calculated as $AUC_{0-6(Day10)}/AUC_{0-6(Day1)}$

Pharmacokinetic parameters of maltol and maltol glucuronide will be listed by dose group for each individual subject and summarized by dose group using the following descriptive statistics: n (the number of subjects), arithmetic mean, SD (standard deviation), geometric mean, geometric CV (coefficient of variation), median, minimum and maximum.

Plasma concentration-time courses of maltol/maltol glucuronide on Day 1 and Day 10, including C_{trough} , will be tabulated and graphically displayed per subject and summary statistics will be provided for each dose group for a specific timepoint/day. Plots of mean and geometric mean and plots with combined individual time courses will be provided by dose group.

Actual and/or dose-normalized pharmacokinetic parameters of C_{max} and AUCs will be graphically displayed for maltol and maltol-glucuronide as function of the dose, to explore dose-proportionality.

Serum iron and TSAT:

The following parameters for serum iron and TSAT on Day 1 will be derived for each subject based on the uncorrected and baseline-corrected predicted serum iron concentrations and TSAT, if applicable:

Table 6 Parameters for Serum Iron and TSAT on Day 1

Parameters	Description
C_{\max}	Maximum plasma concentration directly from data
C_{trough}	Pre-dose plasma concentration
Change from C_{trough} to C_{\max}	$C_{\max} - C_{\text{trough}}$
T_{\max}	Time to reach C_{\max}
λ_z	Apparent first-order terminal elimination rate constant
AUC_{0-6h}	Area under the plasma concentration versus time curve from time zero to 6 h using the pre-dose adjusted concentration data
$AUC_{0-\infty}$	Area under the plasma concentration versus time curve from time zero extrapolated to infinity time using the pre-dose adjusted concentration data
CL/F	Apparent clearance calculated as Dose/ $AUC_{0-\infty}$
V_z/F	Apparent volume of distribution (as Dose/ $[\lambda_z * AUC_{0-\infty}]$)

The following parameter for serum iron and TSAT on Day 10 will be derived for each subject based on the uncorrected and baseline-corrected predicted serum iron concentrations and TSAT, if applicable:

Table 7 Parameters for Serum Iron and TSAT on Day 10

Parameters	Description
Tau	The dosing interval for steady-state data tau=12
C_{\max}	Maximum concentration between dose time and dose time + Tau. If not unique, then the first maximum is used.

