C_{trough}	Minimum concentration between dose time and dose time + Tau
Change from C_{trough} to C_{\max}	$C_{\max} - C_{\text{trough}}$
AUC_{0-6h}	Area under the plasma concentration versus time curve from time zero to 6 h using pre-dose adjusted concentration data
$AUC_{0-\tau}$	Area under the plasma concentration versus time curve from time zero to Tau
$C_{\text{ave}(0-6h)}$	Average Steady State Plasma Concentration from 0-6h, calculated as AUC_{0-6h} divided by 6
CL/F	Apparent clearance calculated as Dose/ $AUC_{0-\tau}$
$R_{C_{\max}}$	Accumulation ratio based on maximum concentrations after first dose and last dose, calculated as $C_{\max\text{Day10}}/C_{\max\text{Day1}}$
$R_{AUC0-6h}$	Accumulation ratio based on AUC_{0-6} after first dose and last dose, calculated as $AUC_{0-6(\text{Day10})}/AUC_{0-6(\text{Day1})}$

Pharmacokinetic parameters of serum iron and TSAT will be listed by dose group for each individual subject and summarized by dose group using the following descriptive statistics: n (the number of subjects), arithmetic mean, SD (standard deviation), geometric mean, geometric CV (coefficient of variation), median, minimum and maximum.

Concentration-time courses of serum iron and TSAT on Day 1 and 10, including C_{trough} on Day 1 and 10 will be tabulated and graphically displayed per subject and summary statistics will be provided for each dose group and visit/timepoint. Plots of mean and geometric mean and plots with combined individual time courses will be provided by dose group.

Actual and/or dose-normalized pharmacokinetic parameters of C_{\max} and AUCs will be graphically displayed for serum iron and TSAT as function of the dose, to explore dose-proportionality.

If the PPK model is not feasible for TSAT and PPD model is used for TSAT, the following parameters for TSAT on Days 1 and 10 will be derived for each subject based on the predicted TSAT, if applicable:

Table 8 Parameters for TSAT on Days 1 and 10

Parameters	Description
Baseline	Baseline response value before dosing
R _{max}	Maximum response value
R _{min}	Minimum response value
T _{max}	Time to reach R _{max}
T _{min}	Time to reach R _{min}
AUC _{0-6h}	Area under the effect versus time curve from time zero to 6 h
AUC _{0-24h}	Area under the effect versus time curve from time zero to 24 h
AUC_Above_B	Area under the response curve that is above the baseline
AUC_Below_B	Area that is below the baseline and above the response curve
AUC_Net_B	= AUC_Above_B - AUC_Below_B

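### SD, geometric CV and range of the primary PK parameters come from individual model predictions, so in expectation they understate between-subject variability by an amount set by ETA shrinkage

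*SAP*

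**What the plan says.** The steps are set out in SAP 8.5.4. Profiles for serum iron, maltol, maltol glucuronide and TSAT on Days 1 and 10 "will be predicted for each subject using the individual PK parameters estimates from the final model". Then: "Standard non-compartmental methods (NCA) will be used for the PK parameter calculations based on the predicted concentrations". The maltol and glucuronide parameters are summarised by dose group with, among others, "arithmetic mean, SD (standard deviation), geometric mean, geometric CV (coefficient of variation), median, minimum and maximum". The same is planned for iron: "Pharmacokinetic parameters of serum iron and TSAT will be listed by dose group for each individual subject and summarized by dose group", with the same list of statistics.

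The model is a NONMEM mixed-effects model fitted by FOCEI, with FOCE or FO as fallback (SAP 8.5.1). The SAP does not use the term, but individual estimates from such a fit are empirical Bayes (post hoc) estimates. One of the four stability checks in SAP 8.5.1 is, in per cent, "Shrinkage for interindividual variability terms (ETA) and residual unknown variability (EPS) < 30"; Protocol 12.2.1 has the same limit. Neither document gives the scale or says what happens if the limit is missed.

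Sampling is sparse. After a pre-dose sample, each child has "further PK blood samples collected at two additional times between 0.5h and 6h after dosing on Days 1 and 10" (SAP 4.2.1), on the same schedule both days.

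The SAP does not commit to reporting the model's between-subject variances (OMEGA), to simulating from them, or to showing shrinkage beside the summary tables. The list for observed concentrations in SAP 8.4 has no SD or CV, although the general default in 6.2 includes SD and the rule for values below quantification in 8.3 mentions SD and %CV.

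**The concern.** When a child contributes few samples, the individual estimate borrows from the population mean. The estimates then vary less between children than the true parameters do. SD, geometric CV, minimum and maximum computed from them inherit that compression, while the tables present them as plain descriptive statistics. The geometric means are not in question.

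These are primary-endpoint parameters, and Protocol 5.5 says the study's data will be used to choose the dose or doses for the Phase 3 paediatric study. A reader who takes the tabulated CV as the between-subject CV would expect children on one dose to be more alike than they are.

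**Working it through.** **Design figures.** Neither document has a precision calculation to reproduce; SAP 13 says no formal one was done. The design counts agree: 4 schedules × 3 children = 12 per dose, and 3 × 12 = 36. Blood volume confirms three draws per PK day: screening 1 + 5 = 6 mL; Day 10 safety 1 + 2.5 = 3.5 mL; PK 6 draws × (3 + 5) = 48 mL; total 57.5 mL, as in Protocol 10.7.5. Each child therefore gives four post-dose samples over the two days.

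**Direction.** In a correctly specified model, variance of the individual estimates = true variance − mean posterior variance. The second term is positive, so the spread is too small in expectation.

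**Size for a given shrinkage.** Input: between-subject CV of AUC about 27% in adults (Protocol 12.1), taken as log-normal and wholly unexplained by covariates.

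- ω = √ln(1 + 0.27²) = 0.265.
- SD-scale shrinkage S: SD of individual estimates = (1 − S)ω. Variance-scale: √(1 − S) × ω.
- Geometric CV = √(exp(SD²) − 1).
- Example, S = 30% on the SD scale: 0.70 × 0.265 = 0.186, so the CV is 18.7%.

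| S | Reported CV, SD scale | Reported CV, variance scale | True CV if 27% is reported (SD scale) |
|---|---|---|---|
| 5% | 25.6% | 26.3% | 28.5% |
| 10% | 24.2% | 25.6% | 30.1% |
| 20% | 21.5% | 24.1% | 34.1% |
| 30% | 18.7% | 22.5% | 39.3% |

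**How much shrinkage to expect.** This was simulated with a one-compartment oral model and the four SAP schedules, using post-dose samples only. Half-lives were 0.8 h (maltol) and 1.1 h (glucuronide), with Tmax 1.0 h, from Protocol 5.4. Assumptions not in the documents: 27% variability on both CL and V, ω of 0.5 on ka, residual SD 0.1 to 0.5 on the log scale, population parameters known, each analyte fitted alone, 240 subjects per scenario. SD-scale shrinkage of log AUC(0-6h):

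| Residual SD | Both days fitted | One day only |
|---|---|---|
| 0.1 | 4-9% | 9-10% |
| 0.2 | 10-18% | 22-24% |
| 0.3 | 16-19% | 35-38% |
| 0.4-0.5 | 26-36% | 40-46% |

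The spread of the individual estimates was below the truth in all 20 scenarios. At residual SD 0.2 with both days, 10% shrinkage gives a CV of 24.2%, and 18% gives 0.82 × 0.265 = 0.218, a CV of 22.0%. For Cmax with both days, shrinkage was 6-13% at residual SD 0.1 and 30-44% at 0.5.

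**Effect of covariates.** Spread explained by covariates is not shrunk. If covariates explained half the log-variance (an illustration), 30% shrinkage on the rest would leave 0.5 + 0.5 × 0.49 = 0.745 of the variance. The SD is √0.745 × 0.265 = 0.229, a CV of about 23%.

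**Sampling noise.** The relative standard error of an SD from 12 subjects is about 1/√22 = 21%.

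**The case against.** A reader might infer that the tables will show about 19% where the truth is 27%. The documents do not support that. Thirty per cent is a limit for acceptance, not a forecast, and on the variance scale it gives 22.5%. Four post-dose samples per child, simultaneous modelling of maltol and glucuronide (SAP 8.5.1) and covariates including body weight (SAP 8.5.3) may all reduce the effect. Weight may matter here, because fixed doses are given across a broad weight range (Protocol 5.5). At 5% shrinkage the effect is trivial. The 21% sampling error of an SD exceeds a 10-18% bias, so a single table may by chance not show it. All of this stands. It limits the size but does not change the direction.

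A reader might also infer that the three doses will look better separated, or the exposure tails safer, than they are, and that dose selection will suffer. This is plausible but not shown. The SAP plans no test, interval or separation criterion between doses; the documents give no exposure limit; and they do not say that SD or CV will drive the choice. The 27% applies to maltol and glucuronide. Protocol 5.4 reports no clear relationship between their exposure and serum iron or TSAT, and no between-subject CV is given for the iron measures.

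Finally, observed values are listed and plotted, with minimum and maximum by window, and a modeller may report OMEGA by custom. That helps, but it is not a substitute. Windows hold only 3 or 6 children per dose, the values include residual error, and concentrations by window do not give the spread of AUC or Cmax.

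**Conclusion.** The concern holds as a bias in expectation of uncertain size. As written, the summaries in SAP 8.5.4 understate between-subject variability to the extent of ETA shrinkage; EPS shrinkage plays no part. For a true CV of 27% with none of it explained by covariates, the reported figure runs from 25.6% at 5% shrinkage to 18.7% at 30% (SD scale). About 22-24% is the more likely range for AUC if residual error is near 20% and both days are fitted together. The 18.7% is a bound only if the limit is met. In the simulation, log-AUC shrinkage reached 26-36% at residual SD 0.4-0.5, and ETA shrinkage for V was 33-64% in every both-days scenario, so the plan's silence on what follows a failed check matters. For serum iron and TSAT the direction is the same, but the documents give no basis for a size. This is a reporting weakness in the variability statistics that should be corrected; it does not undermine the central estimates.

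**What to change.** Amend SAP 8.5.4 as follows:

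- Report between-subject variability from the estimated OMEGA, with its standard error, as the main variability result.
- Keep the individual listings and summaries, print ETA shrinkage per parameter beside them, state its scale (SD or variance), and label their SD and CV as shrunken.
- Where exposure spread by dose is used for Phase 3 dose selection, derive it by simulating from the final model with OMEGA and the enrolled children's covariates.

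The cost is SAP wording and one simulation from a model that will already be fitted; no new data are needed. The downside is that OMEGA is itself imprecise with 36 children. Even if every child's parameters were known exactly, the relative standard error of an SD would be about 1/√70 = 12%, and sparse sampling will make it larger. That is why the standard error should be shown.
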